Tacrolimus is the most commonly utilized calcineurin inhibitor after kidney transplantation. It is used in combination with mycophenolate mofetil and prednisone in order to provide sufficient immunosuppression to prevent acute rejection of transplanted organs. The development of a MeltDose tablet formulation has been designed to enhance the bioavailability of tacrolimus due to the low water solubility of the drug. In clinical trials, the utilization of MeltDose tablet formulations of tacrolimus has been shown to provide rapid achievement of target tacrolimus trough concentrations. This once daily dosing regimen has also led to lower peak concentrations and equivalent overall exposure when compared to immediate release and other extended release formulations of tacrolimus. Similar efficacy and safety profiles have been demonstrated when comparing the MeltDose formulation of tacrolimus to other available formulations.

Some transplant recipients have been shown to metabolize tacrolimus at a higher or lower rate compared to other patients, which can greatly impact post-transplant outcomes. This can be prompted by the patient having polymorphisms of the cytochrome P450 3A5 (CYP3A5) gene that they may possess more so compared to others. If a patient is a CYP3A5*1 allele expressor, this leads to metabolically active CYP3A5 causing higher metabolism rates of tacrolimus. CYP3A5 expressors can require up to 2-fold higher tacrolimus doses to achieve similar trough concentrations compared to CYP3A5 non-expressors. This sparks the question as to what the optimal initial dosing of the MeltDose formulation of tacrolimus should be when used in the *de novo* setting for kidney transplant patients. Delayed achievement of target tacrolimus trough concentrations has been linked to higher rates of acute rejection as well as development of *de novo* donor-specific antibodies. Avoiding subtherapeutic and supratherapeutic concentrations of tacrolimus in the early post-transplant period will help to lower risk for acute rejection.

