Study enrollment and informed consent process will begin once IRB approval is granted. Each subject will be active in the study until their one month visit—occurring day 30 +/- 5 days. We anticipate it will take 12 months to enroll the first 35 subjects. After the first 35 subjects are enrolled, an interim analysis will be performed to evaluate the efficacy and safety of the initial dose provided. A report of results will be distributed to Veloxis Pharmacueticals® to assess the efficacy and safety of the utilization of tacrolimus extended-release. A statistical analysis will be completed to identify the correlation with achieving a therapeutic tacrolimus trough concentration with using tacrolimus extended-release in the de novo setting. If required, an additional 35 patients will be enrolled. We anticipate that after enrollment of all subjects, data analyses will be completed 3-6 months after recruitment has ceased.

d) Study Procedures and Data Analysis

Study procedures:

This study is a single center prospective observational study conducted at Temple University Hospital (TUH). All participants will be consented for all procedures involved in this study. This study will utilize the QUEST questionnaire (attached) to evaluate the severity of tremors at 1 month. Data to be collected includes tacrolimus trough levels, study drug dosing, hemoglobin A1c, incidence and severity of tremors, potassium, glomerular filtration rate, and rejection episodes (See Table B).

Table C

Day 0	Study drug (tacrolimus) initiated at 0.13/mg/kg/day for all patients (the day of initiation decided per transplant surgeon discretion)
Day 0-4	Inpatient laboratory parameters checked every 24 hours per Tables A and B
Day 4-30	Outpatient laboratory parameters checked three times weekly on Monday, Wednesday, and Friday per Tables A and B
Day 30 visit (+/- 5 days)	Draw tacrolimus trough levels, serum creatinine, estimated glomerular filtration rate, serum potassium, and blood glucose. Complete tremor questionnaire with participant.
During or prior to Day 30 visit	Oral swab performed to be analyzed for testing of metabolic enzymatic activity (This will be performed to determine ability of the patient to metabolize tacrolimus)

Data and Specimen Banking:

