demographic information, comorbidities related to transplant, cause of kidney disease, incidence and severity of tremors, study drug dosing, other immunosuppressants prescribed, relevant labs (e.g., Cr, K, eGFR, HbA1c, blood glucose, tacrolimus level) and all other pertinent prospective data (e.g., rejection episodes). Only prospective data created between Day 0-Day 30 visit will be collected for the purpose of this research—no retrospective data will be collected. All PHI will be removed from this dataset and subjects will be assigned an arbitrary study ID number. This de-identified dataset will be kept in a separate locked drawer and locked office accessible to only research staff and entered into encrypted password-protected online database, Research Electronic Data Capture (REDCap™, ©Vanderbilt University). Access to REDCAP™ will be granted to [name], BCPS, [name], BA, BSN, RN, [name], and [name] MD, CM, FACS, FRCSC. Documents containing personal health information (e.g., consent, HIPAA form) will be kept in a separate locked drawer in a locked office accessible only to study investigators. Raw data will be exported into a password-protected Excel data sheet stored on Temple hospital computer in a locked research space for data analysis.

Data analysis will be performed by study staff with the assistance of a hospital appointed statistician. From REDCap, raw data will be exported into an Excel sheet and analyzed in SPSS®, version 21.0 for Windows (SPSS, Inc., Chicago, IL). Continuous data such as baseline demographics and laboratory values that are normally distributed will be presented as mean (SD) and non-normally distributed data as median (25-75% interquartile range). Other baseline characteristics and outcomes will be analyzed with the following tests: Chi-square or Fisher's exact tests for categorical data, and Student's T-tests or Mann-Whitney U tests for continuous data. Kaplan Meier statistical testing will be utilized to evaluate time to therapeutic trough concentration. Subgroup analysis stratified by CYP3A5 genotype will be performed. All tests will be two-tailed, and p-values < 0.05 will be considered statistically significant.

e) Withdrawal of Subjects

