***Dosing strategies for de novo once-daily extended release tacrolimus (LCPT) in kidney transplant recipients***

**NCT Number: 03713645**

**Date: August 21, 2018**

Descriptive statistics were used to characterize the baseline demographics of the entire cohort (intent to treat population). Continuous parametric data are presented as mean  $\pm$  standard deviation while continuous non-parametric data are presented as median (25%-75% interquartile range). Analysis of outcomes according to CYP3A5 expresser status within the modified ITT population were completed using the Kruskal-Wallis or ANOVA test for continuous data and the chi-squared test for categorical data. Tests were corrected for multiple comparisons as necessary utilizing the Bonferroni method. All tests were two-tailed, and  $p < 0.05$  was used to represent statistical significance. Time to therapeutic tacrolimus trough concentration was analyzed using a Kaplan-Meier time-to-event analysis. All analyses were performed using SPSS, version 26 for windows (Armonk, NY; IBM Inc.).

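### Replace the SAP's Bonferroni correction with Holm over a stated family of tests: same family-wise error rate, never fewer rejections, and a gain confined to second and later findings

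*SAP*

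**What the plan says.** The SAP is a single unnumbered paragraph. Its genotype analysis is "Analysis of outcomes according to CYP3A5 expresser status within the modified ITT population", "completed using the Kruskal-Wallis or ANOVA test for continuous data and the chi-squared test for categorical data". Its multiplicity rule is "Tests were corrected for multiple comparisons as necessary utilizing the Bonferroni method", with two-tailed tests at 0.05. It plans no simultaneous confidence intervals.

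Protocol section 8(d), Data analysis, lists "T-tests or Mann-Whitney U tests for continuous data" for baseline characteristics and outcomes. It then states separately: "Subgroup analysis stratified by CYP3A5 genotype will be performed". It sets the level as "All tests will be two-tailed, and p-values < 0.05 will be considered statistically significant" and has no multiplicity rule.

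Protocol section 5 describes genotype in two classes: "CYP3A5 expressors can require up to 2-fold higher tacrolimus doses to achieve similar trough concentrations compared to CYP3A5 non-expressors".

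Neither document states how many levels expresser status has, which tests form the family to be corrected, or when correction is needed.

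**The concern.** Bonferroni compares every p-value with 0.05 divided by the number of tests. Holm gives the same protection with thresholds that relax after each rejection, so choosing Bonferroni gives up power for nothing unless its simple simultaneous intervals are wanted.

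The samples are small. Protocol section 8(c) plans 35 subjects and a possible further 35. Section 8(e) lets participants decline the saliva sample, so the genotyped number may be lower. At these sizes, second and later comparisons within a family are the ones likely to be lost.

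The open qualifier 'as necessary' adds a second problem. Whether to correct, and over how many tests, can be settled after the p-values are known.

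**Working it through.** The documents give no power, effect size or SD, so there is no planned figure to reproduce. Steps 1 and 2 need no assumed values. Steps 3 to 5 rest on assumptions that are not in the documents.

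**1. Holm against Bonferroni.** Inputs: family-wise level 0.05, two-sided (both documents); m tests (not stated). Order the p-values p(1) ≤ … ≤ p(m).
- Bonferroni rejects p(j) if p(j) ≤ 0.05/m.
- Holm works upward and rejects while p(j) ≤ 0.05/(m − j + 1).

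Since 0.05/(m − j + 1) ≥ 0.05/m, every Bonferroni rejection is also a Holm rejection. For m = 3 the Holm thresholds are 0.05/3 = 0.0167, 0.05/2 = 0.025 and 0.05; Bonferroni uses 0.0167 three times. For error control, suppose m0 hypotheses are true. The first true one to be rejected faces a threshold of at most 0.05/m0, so the chance of any false rejection is at most m0 × 0.05/m0 = 0.05, whatever the dependence. The first threshold is 0.05/m for both methods, so the gain can come only from the second rejection on.

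**2. Exactly three levels, ANOVA.** Take the omnibus F-test at 0.05 and, if it rejects, pairwise tests at 0.05. If all three means are equal, a false rejection needs a false omnibus rejection (at most 0.05). If just one pair is equal, there is one true pairwise hypothesis, tested at 0.05. The family-wise rate is therefore 0.05 within an outcome. The argument does not extend to four or more groups.

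**3. Size if there are three levels.** Assumed: SD of log dose 0.45; dose ratio 1.5 in both *1 groups, i.e. ln(1.5)/0.45 = 0.405/0.45 = 0.90 SD; groups (non-expressers first) 18/10/7 or 35/20/15. Pairwise t-tests use the pooled ANOVA error. Repeat simulations agreed within about one point.

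| Result | n | Bonferroni | Holm | Omnibus, then pairs |
|---|---|---|---|---|
| Both *1 groups differ from non-expressers | 35 | 18–19% | 23–24% | 35–36% |
| Both *1 groups differ from non-expressers | 70 | 57% | 64% | 75% |
| At least one *1 group differs | 35 | 54–55% | 54–55% | at most the omnibus power, 61–62% |
| At least one *1 group differs | 70 | 89% | 89% | at most the omnibus power, 92% |

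With graded ratios of 1.35 and 1.8, the figures for showing both differences are 19% / 24% / 35% (n=35) and 47% / 57% / 65% (n=70). The gain does not depend on equal shifts.

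**4. Size if there are two levels.** ANOVA is then the t-test (F = t²) and Kruskal-Wallis is the asymptotic Mann-Whitney test. On one simulated data set the p-values were 0.13982 for both of the first pair and 0.13361 for both of the second. No power is lost through the choice of test, and there are no pairs to correct. Holm can act only across outcomes. Assumed: five outcomes, correlation 0.3, groups of 17 and 18, shift 0.8 SD.

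| Outcomes truly different | Average power per outcome, Bonferroni → Holm | At least one, Bonferroni → Holm |
|---|---|---|
| 5 of 5 | 37% → 45% | 80% → 80% |
| 2 of 5 | 37.0% → 38.5% | 56.5% → 56.6% |
| 1 of 5 | 37.6% → 37.7% | 37.6% → 37.7% |

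**5. Adding a separate contrast.** Suppose an any-*1 against no-*1 contrast is tested at 0.05 beside pairwise tests that use another 0.05. With no genotype effect and the group sizes of step 3, the simulated chance of any false rejection is 7.2–7.3% with Holm pairs and 7.5–7.6% with omnibus-then-pairs.

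**The case against.** The best defence is that little is at stake. CYP3A5 is a secondary objective (Protocol section 4), the number of tests is unstated, and Holm does not raise the chance of at least one rejection. All of that stands. It limits the size of the point without giving a reason to prefer Bonferroni. Simple simultaneous intervals would be such a reason, but the SAP plans none.

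A reader might go further and infer three things that the documents do not support.

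- **That the SAP swapped a two-group genotype comparison for an unordered multi-group one and so lost power.** Kruskal-Wallis, ANOVA and a correction do suggest more than two groups, but expresser status may have two levels, as in Protocol section 5, and then nothing is lost (step 4). The protocol does not tie its t-test and Mann-Whitney list to genotype. Bonferroni may be meant for several outcomes and not for genotype pairs.
- **That a single any-*1 contrast is generally more powerful.** It depends on the pattern. At n=35 under the step 3 assumptions, contrast against omnibus is 73% against 61–62% with equal shifts and 75–76% against 74% with graded shifts. With ratios of 1.1 and 2.0 it is 51–58% against 86%, so the contrast loses.
- **That the study is likely to miss the expresser effect.** For a 2-fold dose difference with an assumed CV of 40% to 70% and groups of 5/12/18, omnibus power is 99.7% down to 79.8%, and contrast power 99.9% down to 88.3%.

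**Conclusion.** The point holds in a narrow form. Holm is at least as powerful as Bonferroni at the same family-wise error rate, whether the family is genotype pairs or outcomes. That conclusion needs no assumption about effect size or group sizes.

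The size does need assumptions. In the three-group setting above, Holm adds about 5 points at n=35 and 7 at n=70 to the chance of showing both *1 differences; omnibus-then-pairwise testing adds about 17 and 18. Across five outcomes and two groups, Holm adds 0 to 8 points to average power per outcome at n=35. It adds essentially nothing to the chance of at least one finding. The SD, ratios, group sizes, number of outcomes and correlation are all assumed, and a three-way genotype split is itself an assumption.

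The unstated family matters alongside the choice of method, because neither procedure is defined until its tests are listed.

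**What to change.** In the SAP's multiplicity sentence, replace the Bonferroni method with the Holm step-down method. In place of 'as necessary', state before results are seen:
- the number of levels of CYP3A5 expresser status;
- the tests that form each family (genotype pairs within an outcome, a named list of outcomes, or both).

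Holm must cover the same family that Bonferroni would have covered. If that family spans outcomes, narrowing it to pairs within an outcome would remove protection: four independent outcomes each at 0.05 give 1 − 0.95⁴ = 18.5%.

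If status has exactly three levels and the analysis is ANOVA, the omnibus test at 0.05 followed by pairwise tests at 0.05 may be named instead, within an outcome. Any correction across outcomes would still have to be stated. Do not add an any-*1 contrast at an uncorrected 0.05 beside the pairwise tests (step 5).

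The cost is wording only. Holm uses the same p-values and needs no new data. It gives up simple simultaneous confidence intervals, which the SAP does not plan. If p-values have already been seen, report the change of method as made afterwards.

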Dosing strategies for de novo once-daily extended release tacrolimus (LCPT) in kidney transplant recipients

NCT Number: 03713645

Date: August 21, 2018

1) Abstract of the study

Outcomes after kidney transplantation have been significantly enhanced with the advances made in immunosuppressive therapies. Tacrolimus is currently marketed as an extended-release once-daily formulation dosing option for patients, decreasing pill burden and possibly decreasing adverse effects. Some transplant recipients have been shown to have higher dosage requirements. According to the literature, this can be linked to genetic disparities in the metabolism of tacrolimus.. This potential complication, where differences on specific genes alters metabolism of tacrolimus, can increase difficulty in getting to a therapeutic drug level for immunosuppressants and is one large factor that contributes to the fact that kidney transplant survival rates differ between patients. Due to the enhanced bioavailability of MeltDose formulation once-daily extended-release tacrolimus, its de novo use in recent research and practice has been shown to expedite achievement of target tacrolimus trough concentrations. De novo use of once-daily tacrolimus formulations is understudied. Through a prospective investigational study, we aim to determine the optimal strategy for de novo dosing of once-daily extended release tacrolimus (MeltDose formulation) for kidney transplant recipients at Temple University Hospital.

2) Protocol Title

Dosing strategies for de novo once-daily extended release tacrolimus (LCPT) in kidney transplant recipients

3) Investigator(s)

Principal Investigator(s): [name]. BCPS

Co-PI: [name] [name], CM, FACS, FRCSC

4) Objectives

Primary Objectives:

Identify the target dose of de novo once-daily MeltDose formulation of tacrolimus that achieves therapeutic tacrolimus trough concentrations for kidney transplant patients at Temple University Hospital

Secondary Objectives:

Identify the time to achievement of therapeutic trough concentrations for the de novo MeltDose formulation of tacrolimus

Identify if the CYP3A5 genetic allele is expressed in enrolled participants to retrospectively determine correlation between CYP3A5 genotype expression and other factors (e.g., time to trough, tacrolimus dosing, patient outcomes, demographics) in kidney transplant patients

5) Rationale and Significance

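### The SAP applies Bonferroni only where necessary, without saying to what; a stated family tested with Holm's procedure would close the gap with at least as much power

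*SAP*

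**What the plan says.** The protocol, section 8(d), Data analysis, sets one rule: "All tests will be two-tailed, and p-values < 0.05 will be considered statistically significant". It mentions no adjustment for multiple testing. The same paragraph adds that "Subgroup analysis stratified by CYP3A5 genotype will be performed", without listing the outcomes.

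The SAP, which carries the same date as the protocol, also uses two-tailed p < 0.05, which "was used to represent statistical significance". On genotype it says: "Analysis of outcomes according to CYP3A5 expresser status within the modified ITT population were completed using the Kruskal-Wallis or ANOVA test" for continuous data, with chi-squared tests for categorical data. The next sentence is "Tests were corrected for multiple comparisons as necessary utilizing the Bonferroni method". The SAP gives no family of tests, no number of tests and no condition that makes correction necessary. It does not say whether 0.05 applies before or after correction.

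The secondary objective in protocol section 4 is open-ended: "correlation between CYP3A5 genotype expression and other factors (e.g., time to trough, tacrolimus dosing, patient outcomes, demographics". Section 8(d), Study procedures, lists the data to be collected as "tacrolimus trough levels, study drug dosing, hemoglobin A1c, incidence and severity of tremors, potassium, glomerular filtration rate, and rejection episodes". Neither document says which of these are tested against genotype.

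**The concern.** The genotype comparison is a stated secondary objective, and many outcomes could be compared by CYP3A5 status. If no correction is made across them, a chance difference on one could be reported as a genotype effect. If Bonferroni is spread over all of them, power falls sharply in a study of 35 patients, with 35 more only if required. The wording permits either course, so the standard for a given p-value is not fixed by the text. The SAP is also written in the past tense, so it does not itself show that the choice preceded the results.

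**Working it through.** The documents give no family-wise error rate, corrected threshold or power figure, so there is nothing of the plan's own to reproduce. The only stated input is the nominal 0.05.

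**Count of outcomes (assumption).** The data list in protocol section 8(d) has 7 items, or 8 if tremor incidence and severity are separate. Time to therapeutic trough, which has its own Kaplan-Meier analysis, adds 1, giving 8 or 9. Creatinine and blood glucose, listed among the laboratory data, add 2, giving up to 11. Table B schedules HbA1c only on the day of transplant, so it may not be an outcome at all. I use 7 to 11.

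**Thresholds the SAP wording permits.**
- No correction: 0.05.
- Bonferroni over pairwise comparisons of three genotype groups (three groups assumed): 0.05/3 = 0.0167.
- Bonferroni over nine outcomes (assumed): 0.05/9 = 0.0056. For 7 and 11 outcomes: 0.0071 and 0.0045.

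A result of p = 0.03 passes the first and fails the others.

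**False positives if outcomes are not corrected.** For k independent true nulls at 0.05, the chance of at least one rejection is 1 − 0.95^k:
- k = 7: 0.302
- k = 9: 0.370
- k = 11: 0.431

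These outcomes are probably correlated. Simulation with equally correlated normal statistics gives, for k = 9, about 0.33 at correlation 0.3 and 0.27 at 0.5. For k = 7 at correlation 0.5 it is about 0.23. Under any dependence the rate for nine cannot exceed 9 × 0.05 = 0.45.

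**Bonferroni against Holm.** Take two outcomes, each with 80% power at two-sided 0.05 (assumed). The standardised effect is 1.960 + 0.842 = 2.802.
- Bonferroni tests each at 0.025, critical value 2.241. Power is Φ(2.802 − 2.241) = 0.712.
- Holm rejects an outcome if its p is below 0.025, or if its p is below 0.05 and the other is below 0.025. With independent tests, power is 0.7123 + (0.8000 − 0.7123) × 0.7123 = 0.7748. At correlation 0.5, simulation gives about 0.76 to 0.77.
- Bonferroni over nine outcomes (0.0056, critical value 2.773) leaves Φ(2.802 − 2.773) = 0.51.

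Holm controls family-wise error under any dependence, as Bonferroni does, and rejects everything Bonferroni rejects.

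**The case against.** The strongest reply is that the correction refers to post hoc pairwise tests. The Bonferroni sentence directly follows Kruskal-Wallis and ANOVA, which are typically used for three or more groups. The protocol had planned t-tests and Mann-Whitney tests, which compare two. On that reading, two groups (expressers and non-expressers, the contrast in protocol section 5) need no correction, and both documents give 0.05. Three groups give 0.0167, and 0.0056 does not arise. This is a plausible reading and may be the intended one. The SAP does not state it, however, and it would leave multiplicity across outcomes uncontrolled.

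A reader might also infer more than the documents support:
- **That the two documents set conflicting significance levels.** They do not. Both state two-tailed 0.05, and the difference is the SAP's undefined correction.
- **That the threshold was chosen after the p-values were seen.** The past tense does not rule this out, but nothing shows that it happened.
- **That there are nine genotype outcomes.** No section lists them, and different sets of nine can be assembled from the same data lists.
- **That Bonferroni is an error.** It is valid. Holm is simply at least as powerful at no extra cost.

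It is also fair to say that the stakes are limited. The genotype analysis is secondary, in a single-centre observational study, and its results do not affect participants' care. No hypothesis test is specified for the primary objective. But neither document labels the genotype comparisons exploratory, and the protocol calls any p below 0.05 significant.

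**Conclusion.** The concern holds as a matter of unspecified scope with a better method readily available. The text does not determine whether a genotype result such as p = 0.03 counts as significant. If outcomes are left uncorrected, the chance of at least one false positive is about 30% to 43% for 7 to 11 outcomes, assuming all are tested, all are null and all are independent. Correlation lowers it, to about 27% for nine outcomes at 0.5. The number of outcomes is my assumption throughout.

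The case for Holm does not depend on that count. It is an improvement under either reading of the SAP sentence whenever more than one test is corrected. With two groups and no correction across outcomes it changes nothing, and the SAP need only say that this is what is meant. The 77% against 71% comparison is an illustration resting on an assumed 80% power. The point affects secondary claims only.

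**What to change.** In the SAP, replace the Bonferroni sentence with wording to this effect: *Genotype comparisons in the following family are tested with Holm's step-down procedure at two-sided 0.05: [named outcomes; and pairwise comparisons of genotype groups, if there are more than two groups]. All other genotype comparisons are exploratory and are reported as estimates with 95% confidence intervals, without a declaration of significance.* Align the significance sentence in protocol section 8(d) with this.

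The sponsor must choose the tested outcomes. Time to therapeutic trough and dose requirement are reasonable candidates, since both appear in the section 4 list ("e.g., time to trough, tacrolimus dosing, patient outcomes, demographics"). That list does not rank its items, so other choices are equally valid. If time to trough is included, the between-group test needs naming, because the SAP gives only a Kaplan-Meier analysis.

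The change needs no new data or patients. Its downside is that outcomes outside the family can no longer be called significant. Because the SAP is written in the past tense, any change to the family or procedure made after results were seen should be reported as such.

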- All kidney transplant recipients at Temple University Hospital will receive a *de novo* combination maintenance immunosuppression regimen. This combination regimen includes **tacrolimus extended-release** and mycophenolate mofetil with or without prednisone. Mycophenolate mofetil and prednisone are started on the day of transplantation. The day of initiation of tacrolimus extended-release is decided per transplant surgeon discretion. **The use of tacrolimus extended-release *de novo* differs from the standard of care. Goal tacrolimus trough concentrations for tacrolimus extended-release are identical to the way that goal tacrolimus trough concentrations are drawn for tacrolimus immediate-release at Temple.** Upon hospital discharge after transplant surgery, patients will be seen in the outpatient abdominal transplant surgery clinic three times weekly. **Table B portrays the laboratory parameters that are drawn per research protocol which is identical to laboratory parameters drawn for all kidney transplant patients at Temple University Hospital (Refer to Table A).** Average length of inpatient stay is expected to be 4 days. Table 2 portrays the timeline of data collection. **The data collected that differs from standard of care includes the QUEST Tremor Questionnaire at Day 30 and the required oral swab for testing of CYP3A5 metabolic enzyme activity.**

Table B

Setting	Tacrolimus extended-release trough concentration	Serum creatinine	Glomerular filtration rate	Potassium	Blood glucose	Hemoglobin A1C
Day of Transplant		✓	✓	✓	✓	✓
Inpatient (lab parameters obtained every 24 hours; approximately)	✓ (once tacrolimus initiated)	✓	✓	✓	✓	

Days 0-4						
Outpatient (lab parameters obtained three times weekly on Mon, Wed, Fri; approx Days 4-30)	✓	✓	✓	✓	✓	

Table C

Day 0	Study drug (tacrolimus) initiated at 0.13/mg/kg/day for all patients (the day of initiation decided per transplant surgeon discretion)
Day 0-4	Inpatient laboratory parameters checked every 24 hours per Tables A and B
Day 4-30	Outpatient laboratory parameters checked three times weekly on Monday, Wednesday, and Friday per Tables A and B
Day 30 visit (+/- 5 days)	Draw tacrolimus trough levels, serum creatinine, estimated glomerular filtration rate, serum potassium, and blood glucose. Complete tremor questionnaire with participant.

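### Plain Kaplan-Meier on draw dates ignores the change from daily to Mon/Wed/Fri troughs at discharge, so attainment after about Day 4 is dated up to 2 days late

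*SAP*

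**What the plan says.** Time to therapeutic trough is a secondary objective (protocol section 4): "Identify the time to achievement of therapeutic trough concentrations for the de novo MeltDose formulation of tacrolimus". Another secondary objective relates CYP3A5 genotype to time to trough.

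The draw schedule has two phases. Table B in section 6 gives "Inpatient (lab parameters obtained every 24 hours; approximately" for Days 0-4, and Table C agrees: "Inpatient laboratory parameters checked every 24 hours per Tables A and B". Table B then gives "Outpatient (lab parameters obtained three times weekly on Mon, Wed, Fri; approx Days 4-30". The switch is at discharge: "Average length of inpatient stay is expected to be 4 days". The first-dose day also varies: "The day of initiation of tacrolimus extended-release is decided per transplant surgeon discretion".

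Each document gives the analysis one sentence. Protocol section 8d: "Kaplan Meier statistical testing will be utilized to evaluate time to therapeutic trough concentration". SAP: "Time to therapeutic tacrolimus trough concentration was analyzed using a Kaplan-Meier time-to-event analysis". Neither mentions interval censoring, the change in draw frequency, how the event is dated, whether the event is first or sustained attainment, or a sensitivity analysis. The only hint of a time origin is Table C, which labels drug initiation Day 0.

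**The concern.** A once-daily drug has one trough per day. In hospital all seven per week are measured. After discharge three are, with gaps of 2, 2 and 3 days. Ordinary Kaplan-Meier takes the draw date as the event date, so the same true attainment is dated promptly on the ward and, on some weekdays, late in clinic. The switch falls inside the period being estimated, and at a different time since first dose for each patient.

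Two results are exposed. The first is the estimated time itself, which is what the objective asks for. The second is the CYP3A5 contrast. Protocol section 5 says that expressers can need up to twice the dose. If they therefore reach goal later, more of their events fall in the sparse phase, and their delay is overstated relative to non-expressers.

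**Working it through.** **Inputs.** From the protocol: daily draws to discharge at about Day 4, then Mon/Wed/Fri to Day 30; 35 patients, with a possible further 35. The documents give no expected time to trough, spread or genotype split, so there is no planned figure to reproduce, and every distribution below is an assumption.

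**1. Recording delay.** For true attainment on Mon, Tue, ..., Sun, the wait to the next clinic draw is 0, 1, 0, 1, 0, 2, 1 days. The sum is 5, the mean 5/7 = 0.71 and the maximum 2. Three of seven weekdays have no delay. On the ward the delay is 0. In continuous time the mean waits are (4 + 4 + 9)/14 = 1.21 and 0.50 days, again a difference of 0.71.

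**2. The curve after discharge.** Let F(t) be the true proportion attained by Day t since first dose. Assume lasting attainment, first dose on Day 0, discharge on Day 4 and a random weekday. The recorded proportion is F at the latest draw:

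- Day 5: [3F(5) + 4F(4)]/7
- Day 6: [3F(6) + 3F(5) + F(4)]/7
- Day 7: [3F(7) + 3F(6) + F(5)]/7

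Example: for a lognormal with median 6 days and log-SD 0.5, F(4) = 20.87%, F(5) = 35.77% and F(6) = 50.00%. Day 6 records (150.00 + 107.31 + 20.87)/7 = 39.7%.

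| Assumed attainment | True %, Days 5/6/7 | Recorded % | Shortfall, points |
|---|---|---|---|
| Daily hazard 0.10 | 41.0/46.9/52.2 | 37.2/42.5/48.3 | about 4/4/4 |
| Daily hazard 0.20 | 67.2/73.8/79.0 | 62.6/68.9/75.1 | about 5/5/4 |
| Daily hazard 0.30 | 83.2/88.2/91.8 | 79.1/84.3/89.0 | about 4/4/3 |
| Lognormal, median 3, log-SD 0.5 | 84.7/91.7/95.5 | 77.3/85.8/92.3 | about 7/6/3 |
| Lognormal, median 6, log-SD 0.5 | 35.8/50.0/62.1 | 27.3/39.7/53.2 | about 9/10/9 |

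The range is roughly 3 to 10 points. It is not a bound: a steeper rise just after discharge gives more. Under constant hazard the recorded daily rate falls to 3/7 of the true rate on Day 5, is about 85% of it on Day 6 and is correct from Day 7.

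**3. Does interval censoring remove this?** In 400 simulated samples of 35 with hazard 0.20, the Turnbull estimate averaged 67.1/73.4/78.7% on Days 5/6/7, against the true 67.2/73.8/79.0%. Kaplan-Meier averaged 62.6/68.7/74.8%.

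**4. CYP3A5 contrast.** Mean delay = 0.714 × the proportion attaining after discharge. With log-SD 0.5 and medians of 3 and 6 days, those proportions are 28.3% and 79.1%, giving delays of 0.20 and 0.57 days. The true difference in means is exp(0.125) × (6 − 3) = 3.40 days. It is recorded as about 3.76, an inflation of 0.36/3.40 = 11%. Simulation gave 3.39 and 3.75. Other settings:

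- Medians 4 and 8: 0.714 × (0.917 − 0.500) = 0.30, and 0.30/4.53 = 7%.
- Medians 7 and 14: 0.714 × (0.994 − 0.868) = 0.09, and 0.09/7.93 = 1%.
- Medians 3 and 6, first dose on Day 2: 0.714 × (0.986 − 0.791) = 0.14, and 0.14/3.40 = 4%.

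Across the medians and first-dose days tried, the inflation was about 1% to 12%.

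**5. Medians and the test.** In simulations with log-SD 0.6, N = 35 and discharge on Days 3 to 5, true against recorded medians were 3.5 and 3.5, 4.5 and 4.8, 5.5 and 6.1, 7.6 and 8.3, and 10.6 and 11.3 days. For medians of 3 and 6 with an assumed 18/17 genotype split, the log-rank test rejected in 95.4% of samples with daily draws and 94.8% with the actual schedule. With equal groups (median 5) it rejected in 5.7% and 5.6%.

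**The case against.** The strongest reply is that this is small. In a sample of 35, a bias of 0.36 days in the genotype contrast compares with a sampling SD of 1.06 days. The test is practically unchanged, no false genotype difference is created, and the endpoint is secondary in a single-arm observational study. Kaplan-Meier on draw dates is also a legitimate estimate of time to documented attainment. All of that stands and limits the weight of the point. It does not answer the objective as worded, which asks for the time to achievement.

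A second reply also stands: the documents define neither the event nor a firm time origin, and that gap is more basic than the choice of estimator. The fix must close it too.

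A reader might infer a much larger effect. If each day's trough were in goal independently with probability 0.15, the proportion attained by Day 7 would be 68% with an 8-day stay, 58% with a 4-day stay, and 49% with a 4-day stay and first dose on Day 2. The documents do not support that model. The 0.15 has no source. The titration table in section 6 adjusts doses on measured levels and leaves the dose unchanged at 8 to below 11 for the 8-10 target, so successive troughs should be correlated.

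Nor can one say that patients with longer stays look faster only because they are measured more often. Fewer draws also mean fewer occasions to titrate, which may slow true attainment, and Kaplan-Meier cannot separate the two.

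**Conclusion.** The concern holds, at modest size. The late dating of outpatient attainment follows directly from the stated schedule: 0 to 2 days, mean 0.71. The shortfall of roughly 3 to 10 points on Days 5 to 7 rests on lasting attainment, discharge at Day 4 and the distributions listed. The inflation of the genotype contrast by about 1% to 12% rests on assumed medians and spread. Discharge and first-dose days vary, so in practice the break is blurred around Day 4.

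The documents do not support saying that every later attainer is recorded late, that an observed CYP3A5 difference would be an artefact, or that a median reached before discharge is materially wrong. The change is worth making because it improves the estimate that a secondary objective asks for, at little cost.

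**What to change.** In the SAP:

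- Set the time origin at first dose, and state whether the event is first or sustained attainment.
- For first attainment, record the interval from the last out-of-goal draw to the first in-goal draw. Censor patients never in goal at their last draw.
- Report a Turnbull estimate of the curve and an interval-censored model for CYP3A5 status beside the planned Kaplan-Meier. Label the Kaplan-Meier result first documented attainment.

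A Kaplan-Meier restricted to Mon/Wed/Fri draws for everyone could serve as a sensitivity check on the genotype contrast, but not as an estimate of absolute time, because it delays every patient's recorded time. For the assumed group with median 3 days, the true mean on a daily grid is about 3.40 + 0.50 = 3.90 days. It becomes 3.90 + 0.20 = 4.10 with all draws and 3.90 + 0.71 = 4.61 with Mon/Wed/Fri draws only.

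The cost is SAP wording and a little analysis, possibly in software other than SPSS, with slightly wider estimates. No new data and no change to the draw schedule are needed. If levels move in and out of goal, interval censoring does not recover in-goal days missed between draws, and the report should say so.
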